#### **7.1.5. Final Visit**

When the number of adjudicated primary endpoint events has occurred, a final visit will be conducted for each patient. Study procedures for the final visit will be performed as outlined in the Study Schedule whenever possible ([Attachment 1](#)). At a minimum, vital status must be ascertained for all randomized study participants. All study drug (unused and used syringes) must be returned for adherence and final drug accountability, along with the sharp items container. Investigators should make every effort to contact all patients who are lost to follow-up to ascertain health status by contacting them, their family members, and/or their personal physicians, or by searching national registers or death indices, where permissible by law.

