### **8.3.3. Permanent Discontinuation of Study Drug**

It may be necessary for a patient to permanently discontinue study drug. Investigators should contact the CRO prior to permanent study drug discontinuation. The date of study drug discontinuation will be documented.

Patients who permanently discontinue study drug prior to completing the study will remain in the study to be evaluated for efficacy and safety endpoints and monitored for all visits and testing. If a patient is unwilling or unable to return for future study visits, the site should attempt to collect as much visit information as possible, including through telephone contact, contact with the family or the patient's primary physician, or by searching national registers or deaths indices where permissible by law.

If study drug discontinuation is due to an AE, the event is to be followed according to the procedures in Section 10.2 of this protocol and documented.

Patients will be permanently discontinued from study drug in the following circumstances.

- Enrollment in any other clinical trial involving an investigational product or enrollment in any other type of medical research judged not to be scientifically or medically compatible with this study, and the patient refuses to immediately discontinue from the other clinical trial or medical research.

- The patient's attending physician or the CRO physician requests that the patient permanently stops study drug.
- The patient was inadvertently randomized and, in the opinion of the investigator or the CRO physician, continuation of study drug is not advisable due to safety concerns.
- A patient requires chronic renal replacement therapy (that is, chronic dialysis or renal transplantation).
- A patient is diagnosed with acute or chronic pancreatitis (see Section 10.2.2.1 for criteria to diagnosis acute pancreatitis).
- If after randomization, a patient is observed to have an elevated calcitonin value as described in Section 10.2.2.3.3.1.
- If after randomization, a patient is diagnosed with C-cell hyperplasia or medullary thyroid carcinoma (MTC).
- If an investigator, site personnel performing assessments, or patient is unblinded, the patient must be discontinued from the study drug and the CRO must be notified within one business day.

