4.3.4.3. Censoring Date

For time-to-event analyses (except for mortality analyses), the censoring date for a patient is the Final Visit date if a Final Visit was conducted, the discontinuation date if the patient discontinues from the study early, or the patient's date of death if the patient dies during the course of the study. This censoring date will be used in all analyses (except the mortality analyses) to censor patients who have not experienced the event of interest.

For time-to-event analyses for mortality, the censoring date for a patient is the Final Visit date if the patient is known to be alive at the time of the Final Visit. If the patient discontinues from the study early, the censoring date will be the last date that the investigator can ascertain the patient was alive.

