- 3) **Anti-VEGF therapy** for the treatment of diabetic retinopathy will be defined as an intravitreal injection(s) of an anti-VEGF agent for the treatment of diabetic retinopathy.
- 4) **Clinical proteinuria (macroalbuminuria)** will be defined as an ACR >300 mg/g (>33.9 mg/mmol).
- 5) **Renal replacement therapy (RRT)** will be defined as chronic hemodialysis or
- 6) Peritoneal dialysis used as maintenance therapy in patients with end stage renal disease (ESRD), or renal transplantation.
- 7) **A sustained 30% decline in eGFR** will be based on a 30% reduction from the
- 8) Baseline value (Visit 3) in 2 consecutive calculations of postrandomization eGFR, using the modification of diet in renal disease (MDRD) equation.

Events of laser therapy, vitrectomy, anti-VEGF therapy, or RRT will be prospectively collected. Identification of clinical proteinuria will be based on reported laboratory data (and/or calculated if needed) and eGFR will be calculated using reported laboratory (serum creatinine) and clinical data.

An event of the composite microvascular endpoint is the first occurrence after randomization of an event of diabetic retinopathy requiring laser therapy, vitrectomy for the treatment of diabetic retinopathy, anti-VEGF therapy for the treatment of diabetic retinopathy, development of clinical

proteinuria (macroalbuminuria, see Section 4.17.3), a 30% decline in eGFR (see Section 4.17.3) from baseline, or need for renal replacement therapy.

Time-to-event analyses will be performed for each of the secondary efficacy measures including the individual components of the composite primary endpoint using the ITT population. The analyses of death from CV causes, nonfatal MI, nonfatal stroke, HF requiring hospitalization or hospitalization for unstable angina will be based on adjudicated events. The NNT statistic will be provided for each analysis provided that the p-value from the Cox model is statistically significant. The incidence rate per 100 person-years of follow-up will also be calculated for each type of event.

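### SAP 4.3.4.3 counts time without creatinine or ACR results as event-free for the microvascular composite, so any difference between arms in laboratory sampling would bias its hazard ratio

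*SAP*

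**What the plan says.** **Censoring.** Under SAP 4.3.4.3, "the censoring date for a patient is the Final Visit date if a Final Visit was conducted"; otherwise it is the date of early discontinuation or of death. The scope is general: "This censoring date will be used in all analyses (except the mortality analyses) to censor patients who have not experienced the event of interest". The protocol synopsis likewise censors completers at the end of follow-up, not at the last sample.

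**Detection.** SAP 4.14 applies time-to-event methods to each secondary measure in the ITT population. For macroalbuminuria: "Identification of clinical proteinuria will be based on reported laboratory data". The eGFR component needs a 30% fall "in 2 consecutive calculations of postrandomization eGFR". The other components do not depend on samples: "Events of laser therapy, vitrectomy, anti-VEGF therapy, or RRT will be prospectively collected".

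**Follow-up without visits.** For a patient who has stopped drug and will not return, Protocol 8.3.3 says "the site should attempt to collect as much visit information as possible, including through telephone contact", and also names family, the primary physician and registers. Protocol 7.1.6 allows telephone contact in place of a missed visit. Protocol 7.1.5 says of the last visit: "Study procedures for the final visit will be performed as outlined in the Study Schedule whenever possible". Vital status is the only stated minimum there.

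**Missing data.** The two sensitivity analyses in SAP 4.13.5 cover the primary endpoint only. The deviation in SAP 4.7 for 18 or more months without safety measurements applies only while study drug has not been discontinued. It feeds the per-protocol set, which is not the population for this endpoint.

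**The concern.** A patient whose last creatinine and ACR were taken in year 2, and who is then reached by telephone until a Final Visit in year 6, contributes about four further years as event-free. During those years a laboratory-defined event could not have been seen. That time adds to the denominator and never to the numerator. If one arm has more of it, that arm appears to have fewer renal events, and the multiplicity procedure cannot correct such a difference in ascertainment.

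The SAP follows the opposite principle elsewhere. For mortality after early discontinuation, 4.3.4.3 censors at the last date the patient was known to be alive. Scheduled categorical measures (4.3.3) and the ACR shift tables (4.17.3) require an actual post-baseline value. The laboratory-based time-to-event components have no such rule.

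**Working it through.** **1. The plan's own figures.** The documents give no event count or power for the microvascular composite, so only the primary-endpoint figures can be reproduced. They serve to check the standard-error formula used in step 4.
- Events for HR 0.82, 90% power, two-sided 0.05: 4 × (1.960 + 1.282)² / (ln 0.82)² gives 1068, against 1067 in SAP 4.1.
- Power with 1200 events at alpha 0.0475: 92.7%, against 92.8% stated. Power with 730 events at 0.0081: 51.3%, as stated.

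**2. Simulation of the censoring rule.**
- From the documents: 1:1 allocation; minimum follow-up 5.6 years and enrolment over 2.1 years, hence follow-up uniform from 5.6 to 7.7 years; Cox model with treatment only.
- Assumed: placebo hazard of 3% or 5% per year for the laboratory part and 0.5% per year for retinal procedures and renal replacement therapy (RRT); yearly samples plus one at the Final Visit for attenders. A share of each arm stops giving samples at a uniformly random time but still has a Final Visit date.
- A laboratory event counts only if a sample falls at or after onset. Retinal and RRT events are always captured.
- Size: 1.5 million patients per arm; Monte Carlo error about 0.002-0.003.

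Hazard ratios below are for laboratory hazard 3% / 5% per year.

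| Stop sampling, dulaglutide vs placebo | Unsampled person-time | True HR 1.00: planned rule | True HR 1.00: last-sample censoring | True HR 0.87: planned rule | True HR 0.87: last-sample censoring |
|---|---|---|---|---|---|
| 15% vs 15% | 8.6% vs 8.6% | 1.001 / 1.002 | 1.002 / 1.002 | 0.873 / 0.873 | 0.872 / 0.872 |
| 20% vs 15% | 11.5% vs 8.6% | 0.975 / 0.973 | 1.001 / 1.003 | 0.846 / 0.846 | 0.869 / 0.869 |
| 25% vs 15% | 14.3% vs 8.6% | 0.944 / 0.943 | 0.997 / 1.000 | 0.826 / 0.823 | 0.871 / 0.871 |
| 15% vs 20% | 8.6% vs about 11.5% | 1.029 / 1.032 | 1.002 / 1.003 | 0.897 / 0.902 | 0.873 / 0.875 |
| 15% vs 25% | 8.6% vs 14.3% | 1.055 / 1.062 | 1.000 / 1.001 | 0.917 / 0.926 | 0.868 / 0.872 |

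**3. Closed-form check.** Let f be the laboratory-defined share of events and p the unsampled share of person-time. The null HR is then about (1 − f·p_dula) / (1 − f·p_pbo). With f = 0.03/0.035 = 0.857:
- 11.5% vs 8.6%: 0.9014 / 0.9263 = 0.973 (simulated 0.975).
- 14.3% vs 8.6%: 0.8774 / 0.9263 = 0.947 (simulated 0.944).

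**4. Chance of a nominal two-sided p < 0.05 when the true HR is 1.** The z-statistic shifts by ln(HR) / (2/√events).
- 5-point gap: ln 0.975 / (2/√1825) = −0.54, giving about 8%.
- 10-point gap: ln 0.944 / (2/√1801) = −1.22, giving about 23%.

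**5. Cost of last-sample censoring.** Events fall from 1825 to 1796 (29/1825 = 1.6%) at 20% vs 15%. Across the scenarios the loss is about 1-2%.

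**The case against.** - **Stopping drug is not stopping testing.** A reader might infer that gastrointestinal intolerance would move more dulaglutide patients to telephone follow-up and so create a spurious benefit. The documents do not support that chain. Protocol 8.3.3 keeps patients who stop drug under all visits and tests, and 7.1.4 and 7.1.6 ask for every effort at attendance regardless of adherence. Remote contact is a fallback. No attendance or sampling figures by arm are given, so neither a gap nor its direction is established.
- **Remote follow-up need not mean no results.** Creatinine and ACR are local tests and the endpoint uses reported values. Protocol 8.3.3 includes contact with the primary physician, and exclusion criterion [26] removes patients who refuse such contact. Results may arrive this way, though nothing guarantees them.
- **Some events are found late, not lost.** An ACR still above 300 mg/g is picked up if the Final Visit is sampled. A first eGFR decline seen only there cannot be confirmed, because two consecutive values are needed.
- **The error rates are not the trial's confirmatory error.** In SAP 4.3.6.1 only MACE starts with alpha, and on rejection all of it (0.15 + 0.70 + 0.15 = 1.0) goes to nonfatal MI, CV death and nonfatal stroke. Any alpha for the microvascular endpoint therefore needs MACE and at least one component rejected first. Its weight is in a figure that could not be read here.
- **Last-sample censoring has its own assumption.** It removes the bias only if stopping samples is unrelated to renal risk within arm. It also drops retinal and RRT events after the last sample, gives no follow-up to patients never sampled after randomization, and leaves earlier gaps between samples untouched.

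All five points stand. They limit the size and certainty of the problem and argue against simply replacing the planned rule. They do not supply a rule for unsampled time, and no other section does.

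**Conclusion.** The censoring rule treats unsampled time as event-free for the two laboratory components, by its stated wording. If sampling differs between arms, the composite HR is biased in favour of the arm sampled less: about 3% for a 5-point gap in patients who stop giving samples, and about 5-6% for a 10-point gap. With equal sampling it is essentially unchanged. These sizes rest on assumed attendance and event rates, none of which the documents give. The 8% and 23% error rates hold at nominal 0.05 with about 1800 events, also an assumption, and should not be read as inflation of the trial's gated error rate.

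Nor do the documents show that the microvascular result is biased or that the bias would favour dulaglutide; either direction is possible. The primary endpoint, retinal procedures and RRT are not affected by missing samples. The point concerns one secondary endpoint, but it is cheap to settle before unblinding and hard to settle credibly afterwards.

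**What to change.** 1. For the microvascular composite, prespecify an analysis that ends event-free follow-up at the last visit with both creatinine and ACR reported. Present it beside the 4.3.4.3 version, which keeps later retinal and RRT events.
2. Where a laboratory component is analysed alone, censor at the last result of its own test: ACR for macroalbuminuria, creatinine for the eGFR decline. Keep the 4.3.4.3 date for RRT and retinal procedures, which need no sample.
3. Tabulate missing creatinine and ACR samples, and sampled person-time, by arm.
4. State that last-sample censoring assumes that stopping sampling is unrelated to renal risk within arm, and examine this with an interval-censored or imputation analysis.

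The cost is some SAP wording, derived last-sample dates, a little more analysis work, and about 1-2% fewer events in the last-sample version under the assumptions above. No new data collection is needed.

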4.3.4.4. Handling of Missing Dates

For all adjudicated events, the date the Clinical Endpoints Committee (CEC) indicates the event occurred will be used in all analyses. If this date is missing then the investigator-reported date will be used.

For an incomplete endpoint event (that is, primary endpoint or secondary efficacy endpoint events) date, imputation will be performed as outlined below:

- If only the day of the event date is missing, the day will be imputed as the 15th of the reported month.
- If both the month and day of the event date are missing, the month and day will be imputed as 30 June of the reported year.
- If only the month is missing, the month will be imputed as June.
- In the case that the imputed event date falls after the patient's censoring date as defined above, the incomplete event date will be imputed as the censoring date (for example, if an incomplete onset date of an event is X-X-2012 and the patient's censoring date is 05-22-2012, then the onset date of the event will be imputed as 05-22-2012 rather than as the date of 06-30-2012 as imputed by following the procedure stated above for missing month and day).

For an incomplete death date, imputation will be performed as described below:

- If only the day of the death date is missing, the day will be imputed as follows.
 - (a) If the date of the last reported contact for the patient falls in the same month and year as the death date where the day is missing, the day will be imputed to fall halfway between the last reported contact and the end of the given month (for example, if an incomplete death date is 04-X-2012, and the date of the last reported contact is 04-22-2012, the death date will be imputed as 04-26-2012);
 - (b) If the date of the last reported contact for the patient occurs before the reported month and year of the death date, the day will be imputed as the 15th of the reported month (for example, if an incomplete death date is 04-X-2012, and the date of the last reported contact is 03-26-2012, the death date will be imputed as 04-15-2012).
- If both the month and day of the death date are missing, the month and day will be imputed as follows.
 - (a) If the date of the last reported contact for the patient falls in the same year as the incomplete death date, the death date will be imputed as the first of the month falling halfway between the month of the last reported contact and the end of the year (for example, if an incomplete death date is X-X-2012, and the date of the last reported contact for the patient is 06-22-2012, the death date will be imputed as 09-01-2012).
 - (b) If the year of the last reported contact date for the patient occurs before the year of the incomplete death date, the death date will be imputed as 30 June of the reported year (for example, if an incomplete death date is X-X-2012, and the date of the last reported contact is 06-22-2011, the death date will be imputed as 06-30-2012).

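### SAP 4.3.4.4 sets no floor at randomization for imputed event dates, and one branch of the death rule can fall before last contact

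*SAP*

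**What the plan says.** SAP 4.3.4.4 takes the committee's event date first and the investigator's date if that is missing. It then has two sets of rules for incomplete dates.

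**Primary and secondary endpoint events**
- Day missing: "If only the day of the event date is missing, the day will be imputed as the 15th of the reported month".
- Month and day missing: "the month and day will be imputed as 30 June of the reported year".
- Month missing: "If only the month is missing, the month will be imputed as June".
- Only correction: if the result falls after censoring, "the incomplete event date will be imputed as the censoring date".

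**Deaths**
- Day missing, last contact in the same month: "the day will be imputed to fall halfway between the last reported contact and the end of the given month".
- Day missing, last contact in an earlier month: the 15th.
- Month and day missing, last contact in the same year: "the first of the month falling halfway between the month of the last reported contact and the end of the year".
- Month and day missing, last contact in an earlier year: 30 June.

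The event rules have an upper cap and no lower one. The death rules are each conditioned on last contact and state no upper cap.

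SAP 4.3.4.1 defines time to event as onset date minus randomization date plus 1 day. SAP 4.2 bases the primary and key secondary CV analyses on adjudicated events after randomization. SAP 4.3.4 says every adjudicated event in the locked database is used.

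**The concern.** A cap with a worked example shows that the authors foresaw an imputed date landing outside the patient's follow-up, but only at the far end. At the near end, a true post-randomization event can receive a date before randomization and so a non-positive time.

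The plan does not say what happens next. Under SAP 4.3.4 the event is used, but its time is invalid and SAP 4.3.4.2 turns it into negative person-years. If the condition in SAP 4.2 is applied to the imputed date, a genuine event is left out. That choice would fall to the programmer, for the primary endpoint among others.

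For deaths, the question is whether any branch can return a date on which the patient was known to be alive.

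**Working it through.** **1. Reproducing the SAP's own examples.** Applied literally, the rules return all five.
- Event in 2012, censored 22 May 2012: 30 June is later, so 22 May 2012.
- Death April 2012, last contact 22 April: 22 + (30 - 22)/2 = 26 April 2012.
- Death April 2012, last contact 26 March: 15 April 2012.
- Death 2012, last contact 22 June 2012: month (6 + 12)/2 = 9, so 1 September 2012.
- Death 2012, last contact 22 June 2011: 30 June 2012.

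**2. Events, year only, in the randomization year.** 30 June precedes every randomization date from 1 July to 31 December: 31 + 31 + 30 + 31 + 30 + 31 = 184 dates. Time runs from 0 (randomized 1 July) to -183 days (31 December). For 15 September 2012, 30 June is 77 days earlier, so time = -77 + 1 = -76 days, or -76/365.25 = -0.21 person-years.

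**3. Events, day missing, in the randomization month.** The 15th precedes every date from the 16th on: 365 - 12 × 15 = 185 dates (186 in a leap year). Time runs from 0 to 15 - 31 + 1 = -15 days. Randomized 20 March 2012 with an event in March: 15 - 20 + 1 = -4 days.

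**4. Share of such dates affected.** Assume randomization and event are uniform, with the event on or after randomization in the same year.
- Continuous: (0.5²/2)/(1/2) = 0.125/0.5 = 25%.
- Counting days, 365-day year: (184 × 185/2)/(365 × 366/2) = 17,020/66,795 = 25.5%. Leap year: 25.3%.
- Month rule, counting days: 26.5% to 26.7%.
- Accrual calendar: first visit was planned for June 2011 (Protocol synopsis) and enrollment took 2.1 years (Protocol Attachment 5, overview). With uniform accrual from July 2011, the affected share is (0.125 + 0.125 + 0.045)/(0.125 + 0.5 + 0.42) = 0.295/1.045 = 28%.

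**5. Likely number of events.** The documents do not say how many dates are incomplete. As an illustration, spread 1200 primary events evenly over 6.5 years and assume 1% to 5% have the incomplete form in question.
- Year rule: 1200 × 0.5/6.5 = about 92 events in the randomization year; × 1% to 5% × 25% = about 0.2 to 1.2.
- Month rule: 1200 × (0.5/12)/6.5 = about 8 events in the randomization month; × 1% to 5% × 25% = about 0.02 to 0.1.

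**6. Deaths, every calendar day tried as last contact.**
- Day missing: 0 violations in either branch.
- Year only, last contact in an earlier year: 0 violations.
- Year only, same year, January to October: 0 violations.
- December: (12 + 12)/2 = 12, so 1 December, which precedes last contact on 30 of 31 days. Last contact 20 December 2012 gives 1 December 2012. The largest displacement is 30 days.
- November: (11 + 12)/2 = 11.5. Rounded down this gives 1 November, a violation on 29 of 30 days; rounded up it gives 1 December and none. The SAP does not state the rounding.

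**The case against.** The practical reach is very small. Imputation starts only when the committee's and the investigator's dates leave a gap. Sites report suspected primary events promptly, for example within 2 business days (Protocol 10.1.1). Visits fall at 2 weeks, 3 months and 6 months (Protocol 7.1.4), and events are solicited at every visit after randomization (Protocol Attachment 1, note c). Year-only dates should be rarest in the randomization year, and the same rule applies to both blinded arms. All of this stands. One qualification is that the rules also cover secondary endpoints. Laser therapy, vitrectomy, anti-VEGF treatment and renal replacement are collected prospectively but are not listed among the adjudicated events (SAP 4.14), so no committee date is described for them.

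A reader might infer that deaths in general can precede last contact because only an upper limit is guarded. The documents do not support that. The death rules have the opposite structure: every branch looks to last contact and none has a stated cap. The one failing branch fails because it returns the first of a month.

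A reader might also infer that misdated events would be silently lost. The SAP directs no such thing. SAP 4.3.4 says all adjudicated events are used, so a non-positive time is a visible conflict with the plan. How the Cox software treats such a record is not in the documents.

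**Conclusion.** The gap is real but minor. The event rules produce zero or negative times for 184 possible randomization dates a year (year-only) and 185 or 186 (day missing), and no other section supplies a floor: SAP 4.2 and 4.3.4 settle which events count, not how an imputed date is bounded. The share of about 25% applies only to incomplete dates in the randomization year or month and rests on uniform timing. The event counts above also rest on the assumed 1% to 5%. No effect on the primary conclusion is shown or expected.

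For deaths, the defect is confined to month and day both missing with a last contact in December of the same year, or in November if the half-month is rounded down. One ambiguity remains: CV death and all-cause death are also endpoints, and the SAP does not say which rule set takes precedence. The dedicated death rules are the natural reading. If the event rule were used instead, 30 June would precede any same-year last contact from 1 July on (184 dates).

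**What to change.** Add to SAP 4.3.4.4:
- Imputed event date = max(rule date, randomization date), keeping the existing cap at censoring. The September example becomes 15 September 2012 with time 1 day, and the 184 violations fall to 0.
- Imputed death date = max(rule date, last reported contact date). This removes the 30 affected contact dates a year (59 if the half-month is rounded down).
- The death rules govern all deaths, including those that count as endpoints.

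Use plain floors. A floor one day later can leave the reported period: randomized 31 March 2012 with an event in March would become 1 April, and last contact 31 December 2012 with a death in 2012 would become 2013. The time formula already gives a same-day event 1 day. A floor at the last documented event-free contact should also be avoided: the SAP does not define the term, and it could override a reported month if an event was missed at a contact in between.

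The cost is about one sentence per rule and a line of code each, with no effect on data collection or sample size.
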